2.5. Blinding

The study design was double-blind for the subject, the clinical site and the operational team. The Sponsor was planned to be unblinded to active treatment groups, following the analysis of Month 6 visit data from the main study (18-OBE2109-003 - Edelweiss 3 study), but was to be blinded to the treatment allocated to patients who had previously received placebo.

A database lock was to be performed prior to unblinding of treatment.

2.6. Interim Analyses

Not applicable.

3. STUDY ENDPOINTS

3.1. Efficacy Variables

Primary efficacy endpoints:

The two co-primary, composite, efficacy endpoints are clinically meaningful reduction from baseline to the last 28 days preceding the Month 12 visit (the 4-week period preceding Month 12 visit), along with a stable or decreased use of analgesics for EAP, in the mean daily assessment of 1) DYS and of 2) NMPP, both measured on a Verbal Rating Scale (VRS) using an electronic diary (eDiary).

Secondary efficacy endpoints:

- Change from baseline to Month 12 in DYS (VRS)
- Change from baseline to Month 12 in NMPP (VRS)
- Change from baseline to Month 12 in dyschezia (Numeric Rating Scale NRS)
- Change from baseline to Month 12 in overall pelvic pain (NRS)
- Change from baseline to Month 12 in the interference of pain with the ability to perform daily activities, measured using the pain dimension of the Endometriosis Health Profile-30 (EHP-30)
- Change from baseline to Month 12 in dyspareunia (VRS)
- No analgesics use for EAP during the preceding 4-week period at each scheduled assessment
- No opiate use for EAP during the preceding 4-week period at each scheduled assessment
- Responder rate at scheduled visit other than Month 12 visit, for DYS and NMPP (VRS)
- Change from baseline to each scheduled assessment in the mean pelvic pain scores for DYS, NMPP and overall pelvic pain, during the previous 4-week period assessed on the NRS and VRS
- Change from baseline to each scheduled assessment in the number of days with moderate to severe pelvic pain during the previous 4-week period assessed on the VRS
- Change from baseline to each scheduled assessment in the mean worst pelvic pain score defined as the mean of the 5 highest daily pain scores reported during the previous 4-week period assessed on the NRS
- Change from baseline to each scheduled assessment in the mean of daily dyspareunia scores reported during the previous 4-week period on the dyspareunia VRS
- Change from baseline to each scheduled assessment in the mean of daily dyschezia scores reported during the previous 4-week period assessed on the dyschezia NRS

- Change from baseline to each scheduled assessment in non-opioid, opioid and combined analgesic use for EAP during the previous 4-week period based on pill count in the eDiary
- Change from baseline to each scheduled assessment in opioid analgesic use for EAP as reported in the eDiary during the previous 4-week period based on morphine milligram equivalent (MME)
- Change from baseline to each scheduled assessment in the number of days of analgesic use (including any class) for EAP during the previous 4-week period as assessed in the eDiary
- Change from baseline to each scheduled assessment in the number of days of opioid analgesic use for EAP during the previous 4-week period as assessed in the eDiary
- Change from baseline to each scheduled assessment in the number of pelvic pain-free days (assessed on the VRS) during the previous 4-week period
- Change from baseline to each scheduled assessment in ability to perform daily activities during the previous 4-week period, as assessed in the eDiary (daily function NRS)
- Change from baseline to each scheduled assessment in the number of days with no difficulty in doing daily activities due to EAP during the previous 4-week period as assessed in the eDiary (daily function NRS)
- Change from baseline to each scheduled assessment in the number of days when dyspareunia was a problem during the previous 4-week period (including days when sexual intercourse was avoided because of anticipation of pain) as assessed on the dyspareunia VRS
- Change from baseline to each scheduled assessment in the number of days when sexual intercourse was avoided because of anticipation of pain during the previous 4-week period as assessed on the dyspareunia VRS
- Change from baseline to each scheduled assessment in the number of days with uterine bleeding (including spotting) during the previous 4-week period measured by eDiary
- Change from baseline to each scheduled assessment in the number of days when school or work was missed due to EAP in the previous 4-week period as reported in the eDiary
- Change from baseline to each scheduled assessment in the number of days when the subject had to go to bed or lie down due to EAP in the previous 4-week period as reported in the eDiary
- Change from baseline to each scheduled assessment in the Pain, Control and powerlessness, Emotional well-being, Social support, Self-image dimensions and the Modular sexual relationship questionnaire of EHP-30 scores

- Change from baseline to each scheduled assessment in the Health-Related Productivity Questionnaire (HRPQ) scores
- Number of non-study endometriosis related health visits, number of days in hospital and type of procedures performed based on Health Resource Utilization Questionnaire (HRUQ) at each scheduled assessment
- Change from baseline to each scheduled assessment in the Physician/Subject Surgery Intention Question (PSIQ/SSIQ)
- Change from baseline to each scheduled assessment in the PROMIS Fatigue Short Form 6a
- Change from baseline to each scheduled assessment in the EuroQoL 5-Dimension 5-Level (EQ-5D-5L) questionnaire
- Response at each scheduled assessment according to Patient Global Impression of Change (PGIC) (and Post-treatment Patient Global Impression of Change, PPGIC)
- Change from baseline to each scheduled assessment in the monthly PGIS (mPGIS) score

3.2. **Pharmacokinetic Variables**

PK blood samples will be collected from each subject at each study visit during the Treatment Period for determining linzagolix and KP017 plasma levels.

At the visits where IMP intake is at site, i.e. at Months 6, 7, 8, 9, 10 and 11 visits, PK sampling will be performed before IMP intake. The approximate time of dose administration on the four previous days and time of PK sampling will be recorded in the eCRF.

In case of early discontinuation visit, PK sampling is not required at the withdrawal visit if the subject had no IMP administration the day prior to the withdrawal visit.

Pharmacokinetic analyses will be considered exploratory. Analyses are described in Section 6.4.3.33.

3.3. Safety Variables

Safety endpoints include:

- Change from baseline to each scheduled assessment in BMD measured by DXA of lumbar spine (L1-L4), femoral neck, and total hip
- Incidence and severity of treatment emergent adverse events (TEAEs)
- Incidence and severity of hypoestrogenic TEAEs (hot flush)

CRS-BS-TP-000005 V 2.0

Page 20 of 99

- Time to the first post-treatment menses
- Changes in clinical laboratory assessments (hematology, biochemistry, coagulation parameters, hormones, lipids and urinalysis) from baseline to each scheduled assessment
- Any pathological changes from baseline in the endometrium as assessed by histology from endometrial biopsies
- Changes from baseline to each scheduled assessment in any other safety parameter including weight, vital signs, ECG, gynecological assessments and endometrial thickness

Safety analyses are described in Section 6.6.

3.4. **Exploratory Variables**

Exploratory endpoints include:

- Change from baseline in bone turnover markers at each scheduled assessment
- PK and PD of linzagolix

Exploratory analyses are detailed in Section 6.8 (and Section 6.4.3.33.for PK).

4. ANALYSIS SETS

4.1. Analysis Set Definitions

The following data sets will be used for the statistical analysis:

1. **Treatment Extension Analysis Set (TEAS)**: All subjects from the main study who entered the extension study and received at least one dose of study drug with the exception of subjects whose Month 6 assessments subsequently met any of the discontinuation criteria. These subjects will be withdrawn from study treatment and will enter the Follow-Up Period. Subjects will be analyzed according to randomized treatment.

Discontinuation criteria at Month 6 are the following and will programmatically identified for the analyses sets derivations purpose, based on the Month 6 locked database from the main study, and applying Month 6 analysis visit windows from the main study SAP:

- Endometrial Biopsy: in case of endometrial biopsy diagnosis being an endometrial hyperplasia of any type or worse (malignant endometrial neoplasm) at the Month 6 assessment.
- Serum calcium: Subjects who have a serum calcium level on treatment at the Month 6 assessment above 3.1 mmol/L study treatment are to be interrupted. A repeat test of this parameter within 2 weeks under fasting conditions is to be performed. If the results of the repeat remain above 2.9 mmol/L, study treatment should definitively be discontinued
- BMD loss: subjects who experience more than 8% BMD loss or a Z-score ≤ -2.5 at any site (femoral neck, hip or spine) at the Month 6 assessment.

Per protocol, assessments with BMD loss >5% should be confirmed with a second scan. For assessments with BMD loss "Confirmed (no repeat)" the initial scan will be used to check the discontinuation criteria. The repeated confirmatory scan will be used otherwise. Only confirmatory scans within the +/-28 days window of theoretical Month 6 date will be included.

- Liver function tests: subjects who have an elevation of hepatic enzymes at the Month 6 assessment are to be withdrawn immediately from treatment if:
 - ALT or AST >8xULN
 - ALT or AST >5xULN for more than 2 weeks. Repeats assessments within 2 weeks after the initial assessment will be checked for this criteria.
 - ALT or AST >3xULN and (TBL >2xULN or INR >1.5)
 - ALT or AST >3xULN with the appearance of fatigue, nausea, vomiting, right upper quadrant pain or tenderness, fever, rash, and/or eosinophilia (>5%)
- ECG: subjects who have a QTcF > 500 ms at the Month 6 assessment or increase > 60 ms from the highest value prior to the first dose in the main study

2. **Per Protocol Extension Analysis Set (PP EAS)**: All subjects from Treatment Extension Analysis Set, excluding those identified as having major protocol deviations that could potentially affect the efficacy assessments up to Month 12. Subjects will be analyzed according to randomized treatment.

3. **Follow-up Extension Analysis Set (FU EAS)**: All subjects from the main study who entered the extension study and received at least one dose of study drug with the exception of subjects whose Month 6 assessment subsequently met any of the discontinuation criteria, and who entered the Post-Treatment Follow-Up Period. Subjects will be analyzed according to randomized treatment.

4. **Extension Safety Analysis Set (ESAF)**: All subjects randomized into the extension study who received at least one dose of study drug irrespective of the treatment received. Subjects will be analyzed according to treatment received.

5. **Follow Up Safety Analysis Set (FU SAF)**: All subjects randomized into the extension study who received at least one dose of study drug irrespective of the treatment received, and who entered the Post-Treatment Follow-Up Period. Subjects will be analyzed according to treatment received.

6. **Extension Pharmacokinetic (PK) Set**: all subjects who were randomized and received active study medication in the main study, had no major protocol deviations impacting PK throughout the main study or extension and with available PK data. Subjects will be analyzed according to treatment received.

7. **Extension Pharmacodynamic (PD) Set**: all subjects who were randomized and received active study medication in the main study, had no major protocol deviations impacting PD throughout the main study or extension and with available PD data. Subjects will be analyzed according to treatment received.

In general, analyses of efficacy will be conducted using the TEAS, PP EAS (when specified) and FU EAS sets, analyses of safety will be conducted using the ESAF and FU SAF, and analyses of PK and PD will be conducted using the PK and PD Sets accordingly.

The actual treatment will be derived as follows, based on daily e-diary IMP intake data:

Treatment kits will be dispensed to the subjects as follows:

- on Month 6 and Month 9 visits, subject will receive two kits, one for linzagolix/placebo (monthly kit) and one for the ABT/ABT placebo (3-monthly kit).

- On Month 7, Month 8, Month 10 and Month 11 visits, subject will receive one kit only, for linzagolix/placebo. The number of days with one pink tablet, one grey tablet and one red capsule taken based on e-diary IMP intake data for each treatment will be computed. Data from "Today" will be used primarily. If data from today is missing, data from "Yesterday" of the

following day will be considered. If the e-diary is not completed for a day (neither "Today" nor "Yesterday" of following day), it will be assumed that no intake of drug was taken on that day.

Further rules are as follows:

- Treatment administration errors:
 - If a subject received placebo with placebo ABT on more than 50% of days (even if it is not planned), then the actual treatment group will be placebo with placebo ABT for the extension period.
 - Otherwise, the active treatment (combined with add-back or placebo add-back) with the most days taken will be assigned for the extension period.
 - If the number of days is equal for two treatments groups containing active treatment, then LGX 200 mg with ABT will be assigned for the extension period.
- If a subject discontinued, only data received up to discontinuation will be used.

All analyses for the extension study will be described according to the combined treatment group based on the treatment on the main study and the extension study.

For the combined actual treatment groups, the actual treatment during the main study and the actual treatment during the extension study comprise the following four combined actual treatment groups. It is possible that the derived actual treatment group will not correspond to any of the combined planned treatment groups; thus the combined actual treatment group will be derived as follows:

Actual treatment Main study	Actual treatment Extension study	Combined actual treatment group
Combination planned in the pr	otocol	
Placebo	LGX 75 mg	Placebo / LGX 75 mg
Placebo	LGX 200 mg + ABT	Placebo / LGX 200 mg + ABT
LGX 75 mg	LGX 75 mg	LGX 75 mg
LGX 200 mg + ABT	LGX 200 mg + ABT	LGX 200 mg + ABT
Combination not planned in the protocol (but possible with treatment administration errors)		
Placebo	Placebo	Placebo / LGX 75 mg
LGX 75 mg	Placebo	LGX 75 mg

LGX 200 mg + ABT	Placebo	LGX 200 mg + ABT
LGX 75 mg	LGX 200 mg + ABT	LGX 75 mg
LGX 200 mg + ABT	LGX 75 mg	LGX 200 mg + ABT

4.2. **Protocol Deviations**

A protocol deviation is any noncompliance with the clinical trial protocol or International Conference on Harmonization Good Clinical Practice (ICH GCP) requirements. It was the responsibility of the site investigator to use continuous vigilance to identify and report deviations. All deviations were to be addressed in study source documents and reported to the reviewing IRB/IEC per their policies. The site investigator was responsible for knowing and adhering to the reviewing IRB/IEC requirements.

All Protocol Deviations were to be reported to the Sponsor and documented in the monitoring report. These will be classified as minor or major based on their effect on the right, safety or wellbeing of the subjects and/or the quality and integrity of the data. Major deviations that could potentially affect the efficacy assessments up to Month 12 and thus may exclude subjects from the PP Extension Analysis Set may include:

- Non-compliance with inclusion criteria 2
- Non-compliance with exclusion criteria 2; 3; 4; 6
- IP Dispensing error;
- Randomisation code broken
- Subjects with a gap of at least 28 days between end of treatment in main study and treatment start in Extension
- Non-compliance with study treatment: threshold to be defined during blinded data review meeting (e.g. IMP compliance in tablets <60% for Month 6-Month 12)
- Unauthorised prior or concomitant therapy;
- M12 Visit performed outside the +/-14 days of the theoretical visit date;

The final rating of all deviations will be confirmed prior database lock. The final protocol deviation file (formatted as a Microsoft Excel file) will be provided to Cytel.

Major protocol deviations will be summarized by category and by treatment group on the Treatment Extension Analysis Set.

All protocol deviations will be presented in the data listing. Protocol deviation records with missing subject ID and thus not related to any particular subject will be excluded in the listings.

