13.5.5 Pharmacodynamic analysis methodology

Pharmacodynamic parameters, such as for example estradiol and other hormones, will be summarized by time point for each treatment group, and listed for each subject by visit day and dose regimen. Where appropriate, changes from baseline will be presented. Potential PK-PD relationships may be investigated graphically and through statistical modeling, whilst also exploring possible covariates, and will be reported separately.

PD analyses will be based on the Extension PD Set.

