2.3. Randomization Methodology

Subjects who previously received placebo were randomized in a 1:1 ratio to either linzagolix 75 mg alone (with ABT placebo) or linzagolix 200 mg with ABT), as per the main study randomization schedule.

Subjects who received active treatment continued with the same treatment (linzagolix 75 mg alone or linzagolix 200 mg with ABT).

In order to maintain the blind, the sites were not required to perform any randomization activities. The kits were automatically allocated to the corresponding patients in the IWRS upon confirmation of their eligibility.

2.4. **Stopping Rules**

Subjects were informed that they had the right to withdraw from the study at any time, without prejudice to their medical care, and that they were not obliged to state the reason(s). Any withdrawal must be fully documented in the eCRF exit form.

The Investigator may have withdrawn a subject at any time if this was considered to be in the subject's best interest.

In addition, the sponsor could make a decision to temporarily or permanently discontinue the study for safety, ethical, compliance or other reasons. In this case, the subject's participation was to be ended prematurely without asking for her consent.

In addition, an Independent Data Monitoring Committee (IDMC) regularly reviewed safety data and made recommendations concerning the continuation, modification or termination of the study.

Withdrawal during Treatment Period:

Subjects discontinuing participation in the study during the Treatment Period were to undergo the procedures required at Month 12, except the DXA in case of discontinuation before Month 9 visit. These subjects would enter the 6-month Follow-Up Period and would continue daily eDiary recording for 6 months and up to Month 6 ExFU visit in order to continue to collect efficacy and safety data.

PK sampling is not required if the subject had no IMP administration the day prior to the withdrawal visit.

Withdrawal during Follow-Up Period:

Subjects discontinuing participation in the study during the Follow-Up Period were to undergo the procedures required at Month 6 ExFU visit, which included completion of all ClinRO and ePRO questionnaires, except the DXA in case of discontinuation before Month 3 ExFU visit.

Discontinuation criteria

During the course of the study, the subject may have been discontinued for the following reasons:

During the course of the study, the subject may have been discontinued for the following reasons:

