In the present study, the available US-specific scoring will be used (see Appendix D in Section 9. how to compute EQ-5D-5L crosswalk index values with SAS using the United States value set as an example).

Answers to each dimension will be summarized by category at each visit. The index value and VAS Score will be summarized as continuous variables (actual values and changes from baseline). The EQ-5D-5L items, VSA score and index value at each visit will be presented in a by-subject listings, for both Treatment Extension Analysis Set and Follow-up Extension Analysis Set.

6.4.3.31. Response at each scheduled assessment according to Patient Global Impression of Change (PGIC) (and Post-treatment Patient Global Impression of Change, PPGIC)

Responses to the Patient Global Impression of Change questionnaire range from 0- Very much worse to 6-Very much improved. Responses will be summarized by category at each visit (up to Month 6 Extension follow-up).

6.4.3.32. Change from baseline to each scheduled assessment in the monthly PGIS (mPGIS) score

Responses to the Patient Global Impression of Severity range from 0- No symptoms to 4-Severe. Responses will be summarized by category at each visit (up to Month 6 Extension follow-up).

6.4.3.33. Daily Patient Global Impression of Severity (dPGIS), Daily Event Cancelled, Daily Difficulty Sleeping

The dPGIS, Event Cancelled and Difficulty Sleeping daily diaries were collected for subjects enrolled prior to amended Protocol V4.0 only.

The dPGIS mean scores and changes from baseline, the number of days with difficulty sleeping, the number of days for which events were cancelled and the number of days with no event planned will be computed for each 4-week period and reported in listings only.

The dPGIS scores will be calculated by averaging over the corresponding 28 calendar days immediately prior to and including the day of each scheduled assessment (or prior to and including the last dose date for subjects who discontinue treatment).

6.5. **Pharmacokinetic Evaluations**

Pharmacokinetic analyses will be conducted using the Extensions Pharmacokinetic Set.

PK samples are collected at each monthly visit during the treatment extension period.

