6.6.3. Laboratory Data

Clinical laboratory values will be expressed using conventional SI units.

Hematology, coagulation parameters, chemistry and lipids were assessed at screening and at each visit during the extension treatment period (from M7 to M12), as well as at the M1 ExtFU and M3 ExtFU visits.

E2, progesterone (P4) and LH were assessed at each visit during the extension treatment period (from M6 to M12), as well as at M1 ExtFU and M3 ExtFU visits.

Serum levels of sex hormone-binding globulin (SHBG) were assessed on Month 6, Month 9 and Month 12 visits.

Blood samples were to be analyzed by the central laboratory. Due to the covid-19 situation, some samples may be collected by local laboratories.

For Hematology, coagulation parameters, chemistry and lipids, the actual value, change from baseline and change from baseline 2 (only for the subjects who are in the placebo arm in the

```
CRS-BS-TP-000005 V 2.0
```

main study) will be summarized for each visit for each treatment group. In the event of repeated values, the last non-missing value per study day/time will be used.

Semi-quantitative laboratory results will be imputed as follows: "<X.X" will be imputed as "X.X/2" and ">X.X" will be imputed as "X.X".

Evaluation of shifts for changes from baseline and for changes from baseline 2 (only for the subjects who are in the placebo arm in the main study) to all visits according to the normal ranges with categories "Low", "Normal", "High" where available (for ALT, AST, ALP, Bilirubin, Albumin, Calcium, Creatine Kinase) and according to normal/abnormal/abnormal clinically significant information collected otherwise, will be provided.

For Liver Function Test (LFT) parameters (ALT, AST, ALP, total bilirubin, albumin), evaluation of shifts for changes from baseline will be extended by the worst (highest) on-treatment value (including unscheduled assessments) according to the normal ranges with categories "Low", "Normal", "High" will be provided.

For the lipid panel (Triglycerides, HDL, LDL, Total Cholesterol, LDL/HDL ratio), the percent change from baseline and the percent change from baseline 2 (only for the subjects who are in the placebo arm in the main study) to each on-study visit will also be summarized.

Assessments from local laboratories will not be included in summaries and shift tables, as normal ranges may not be comparable.

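### The Extension PK Set requires active drug in the main study, so placebo switchers drop out of every PK summary although they are sampled on linzagolix at Months 7 to 12

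*SAP*

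**What the plan says.** **Who is in the sets.** SAP section 4.1 (sets 6 and 7) and protocol section 13.4 (sets 4 and 5) define the Extension PK and PD Sets with the same entry condition: "all subjects who were randomized and received active study medication in the main study". The remaining conditions are no major deviation affecting PK (or PD) in either study, and available data.

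**Which set is used.** SAP section 4.1 states that "analyses of PK and PD will be conducted using the PK and PD Sets accordingly". SAP section 6.5 repeats this for PK: "Pharmacokinetic analyses will be conducted using the Extensions Pharmacokinetic Set". Protocol section 13.5.4 also ties PK analyses to the PK Set, and protocol section 13.5.5 says that "PD analyses will be based on the Extension PD Set".

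**Who is sampled and treated.** SAP section 3.2 says that "PK blood samples will be collected from each subject at each study visit during the Treatment Period". SAP section 2.3 says: "Subjects who previously received placebo were randomized in a 1:1 ratio", to 75 mg or to 200 mg with ABT. No extension arm is assigned placebo.

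**How results are shown.** SAP sections 4.1 and 6.2.1 present the extension analyses by four groups that combine main-study and extension treatment. Two of them are the placebo switchers. Section 6.2.1 names pharmacokinetic parameters among the tabulations. For PD parameters, protocol section 13.5.5 says they "will be summarized by time point for each treatment group".

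**The concern.** The entry condition looks back to the main study, while sampling, treatment and the table layout all concern the extension. A switcher takes linzagolix from Month 6 and gives blood for PK at every later treatment visit, but no clause in the definition admits her. Neither document gives a reason. SAP section 7 widens the Follow-up Extension Analysis Set but leaves the PK and PD Sets alone. The Extension Safety Analysis Set, by contrast, does not depend on active treatment in the main study.

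At stake is the descriptive PK summary for two of the four groups. Protocol section 13.5 makes the assessment of switchers a secondary objective, yet the plan would give no tabulated concentrations for them. Anyone programming the tables must either print two empty columns or depart from the set definition without authority.

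**Working it through.** **Inputs**
- Main study: 450 subjects, 150 in each of three groups, one of them placebo (SAP section 2.2).
- Main-study completion 80%, and extension uptake up to 80% of completers (SAP section 2.2).
- Switchers split 1:1 (SAP section 2.3).
- PK samples at Months 6 to 12. At Months 6 to 11 they are taken before that day's dose (SAP section 3.2).
- Assumption, not in the documents: equal completion and uptake across arms. As a range, placebo subjects are taken as 25% to 40% of entrants.

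**Step 1: the plan's own figure.** 450 × 0.80 = 360 completers, and 360 × 0.80 = 288 entrants. Both match SAP section 2.2.

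**Step 2: women excluded.** 288 / 3 = 96 switchers, or 96 / 2 = 48 per switch group. That leaves 288 − 96 = 192 continuing women who can qualify.
- Placebo share 25%: 288 × 0.25 = 72 (36 per group).
- Placebo share 40%: 288 × 0.40 = 115.2, about 115 (about 58 per group).

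**Step 3: scheduled samples, Months 7 to 12 (six visits).** Switchers: 96 × 6 = 576. All entrants: 288 × 6 = 1,728. Share: 576 / 1,728 = 33%. Over the assumed range the switchers' samples number 72 × 6 = 432 to 115.2 × 6 = 691.2, about 691.

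Month 12 counts as on drug. The last dose is taken the day before that visit (protocol section 10.2.1), and SAP section 5.5 accepts Month 12 samples up to 2 days after the last intake.

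**Step 4: the share when Month 6 is counted.** Continuing women are already on drug at their Month 6 sample; switchers are not. On-drug samples: 192 × 7 + 96 × 6 = 1,344 + 576 = 1,920. Share: 576 / 1,920 = 30%. The one-third figure therefore holds for Months 7 to 12 only.

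**Step 5: PK and PD side by side**

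| | PK concentrations | Hormones (E2, P4, LH, SHBG) |
|---|---|---|
| Set named in SAP 4.1 | PK Set (no switchers) | PD Set (no switchers) |
| Set named in the protocol | PK Set (13.5.4) | PD Set (13.5.5) |
| Where the SAP places the summaries | 6.5, on the PK Set | 6.6.3, within safety section 6.6, on the Extension Safety Set (switchers included) |
| Other reporting | Listings of all concentrations (6.5) | Listings; plots of E2 against BMD change from baseline 2, for placebo-arm subjects (6.6.3) |

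For PK, every statement points to a set without switchers. For hormones, the SAP's general sentence and the protocol point one way and SAP section 6.6 points the other.

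**The case against.** The case for leaving the definition alone has some weight. PK and PD are exploratory, no hypothesis is tested, and no efficacy or safety result depends on these sets. Protocol section 13.5 puts the focus on women who had active treatment in the main study, which could be the reason for the restriction. That section does not offer it as one, however, and it also makes switchers a secondary objective. A deliberate exclusion would also need the two empty groups removed from the PK layout, and the SAP does not do this.

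Several stronger readings are tempting, and the documents do not support them:

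- **PD tables with no switchers.** The SAP has no separate PD section and assigns no specific table to the PD Set. Its hormone summaries sit under safety and include switchers.
- **Concentration data thrown away.** SAP section 6.5 lists all plasma concentrations. What is lost is the summary.
- **The modelling loses the same women.** The documents call it a separate exercise, reported separately, and do not state its input dataset. The loss is possible but not established.
- **Irreplaceable information on early exposure.** Within the extension, only switchers are in their first six months on drug. Continuing women had theirs in the main study on the same two regimens. Apart from Month 6, that study's PK schedule is not shown, so what is uniquely lost cannot be judged.

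**Conclusion.** The point holds for PK. As written, the Extension PK Set leaves two of the four planned groups empty in every PK descriptive summary, although these women are sampled on linzagolix at Months 7 to 12. The size is about 96 women (72 to 115 over the assumed range) and up to 576 scheduled Month 7 to 12 samples. These are ceilings. They rest on equal retention across arms, the full 288 entrants, no dropout during the extension, and no samples lost to the PK window rules.

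For PD the finding is narrower: the documents disagree about which set governs the hormone summaries. The SAP carries over the protocol's wording, so the defect is shared and is not an SAP departure. It should be corrected because the plan contradicts its own layout and the data are already scheduled, but it does not touch the primary analysis.

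**What to change.** Redefine both sets in SAP section 4.1 as all subjects who:
- entered the extension;
- received at least one dose of linzagolix in the extension;
- had no major protocol deviation impacting PK (or PD); and
- have available PK (or PD) data.

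Extension entry and an extension dose both need to be stated. A rule based on linzagolix in either study would admit main-study women who never entered the extension, and the present wording, read literally, does not require entry either.

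Summarise PK by the four combined groups, with switchers on drug from Month 7 and their Month 6 sample labelled as pre-active. State one governing set for E2, P4, LH and SHBG, and bring SAP sections 4.1 and 6.6 and protocol section 13.5.5 into line with it. If the exclusion is intended, give the reason and remove the two switch groups from the PK tables.

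The cost is about one sentence per set in the SAP and protocol section 13.4, one sentence on the hormone set, and an entry in SAP section 7. No new data are needed.
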